3.2 Sample Size and Power Considerations

The study will enroll a sufficient number of patients with ADA-SCID who meet all study entry criteria described to assure six (6) patients are evaluable, where evaluable is defined as completing the EZN-2279 treatment period (Week T-21) and providing primary study endpoint data.

More than 6 patients may be enrolled to achieve the required number of evaluable patients. It is expected that up to 12 study centers will participate in the study. There are no restrictions on the number of patients a single study center may enroll.

The sample size of six patients accounts for more than 5% of the entire eligible patient population worldwide and 10% of the entire eligible patient population in the United States.

The patients enrolled in this study all will have achieved metabolic detoxification with weekly Adagen® dosing prior to initiating EZN-2279 treatment. All patients are expected to maintain the target trough total erythrocyte dAXP concentration with EZN-2279. Therefore, the usual statistical sample size calculations using precision analysis, power analysis, or probability are not applicable due to zero variability.

3.3 Randomization

This is an open-label, single-arm study with no randomization.

3.4 Changes to the Design and Study Procedures Proposed in Protocol

None.

4. ANALYSIS POPULATIONS

The analysis populations used to assess the results of this study are described.

4.1 As-Treated (AT) Population

The as-treated population, defined as all patients who are enrolled and receive at least one dose of either EZN-2279 or Adagen[®] Lead-in dosing, will be the primary analysis set in evaluating patient characteristics, treatment administration/compliance and safety.

If, during the Adagen[®] Lead in phase, a patient cannot have his/her Adagen[®] dose adjusted such that inclusion criteria for trough dAXP levels ($\leq 0.02 \mu\text{mol/mL}$) and trough ADA activity ($\geq 15 \mu\text{mol/h/mL}$) levels are met, then this patient will not be eligible to move into the EZN-2279 treatment period (i.e., this patient will have no EZN-2279 treatment and dosing data).

4.2 PK Population

The PK evaluable population, defined as all patients who have received EZN-2279 for at least 9 weeks (i.e. through at least Week T-9) and who have PK data at study week T-9 to indicate exposure, will be the analysis set for evaluating PK parameters.

Patient datasets with samples collected until at least 120hr following dosing of EZN-2279 in Week T-9 will be considered sufficient for PK analysis. Data will be considered insufficient for extrapolation of the terminal phase for determination of PK parameters if the following criteria are met: non-negative slope for the terminal phase; $R^2 < 0.80$ for the determination of λ_z by log-linear regression; less than 3 data points after T_{max} ; extrapolated area-under-the-curve $> 80\%$.

Patients < 10 years of age will not have full PK sampling done due to the blood volume requirements and will only have limited sampling done.

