## 10.6. Pharmacokinetic and Pharmacodynamic Assessments

### 10.6.1. Pharmacokinetic Assessments

Only patients  $\geq 10$  years of age will undergo full PK assessments due to blood volume restrictions in pediatric patients. All patients  $< 10$  years of age will have the same assessments and in lieu of full PK sampling will have limited PK sampling done. Only trough samples along with 48 hours post dose during Adagen Lead In Week T-5 and EZN-2279 Week T-9 will be collected.

Venous blood samples (EDTA tube, up to 2 mL per timepoint) for the determination of the PK profile of EZN-2279 will be collected at Week L-4, after the Adagen® lead-in, and Week T-9 after initiation of EZN-2279 therapy (see Appendix 2). Note: If the dose of EZN-2279 is altered, the full PK profile should be repeated not earlier than 4 weeks after adjustment of the dose of EZN-2279.

**Note:** The site should calculate sample collection dates and times in advance of scheduling a patient's first day of administration, so as to avoid sample collections during non-routine times such as evenings, holidays, etc.

It is extremely important to collect all samples at the times specified. Both the scheduled and actual times of sample collection should appear on the sample collection record used in the clinic. In addition, the actual times at which the infusion is started and stopped must be recorded.

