#### 13.2.3.6. Pharmacokinetic Data Analysis

Pharmacokinetics of EZN-2279 and Adagen® will be based on plasma concentrations of ADA activity. The concentration of ADA activity in all collected samples will be determined by a validated assay. The following PK parameters (secondary endpoints) will be computed from individual plasma concentrations using appropriate validated PK software.

- $C_{max}$  Maximum observed drug concentration
- $C_{trough}$  Concentration minimum before repeat dosing
- $t_{max}$  Time of the maximum drug concentration (obtained without interpolation)
- $AUC_{(0-t)}$  AUC calculated using linear trapezoidal summation from time zero to time t, where t is the time of the last measurable concentration ( $C_t$ )
- $K_{el}$  Terminal elimination rate constant calculated by linear regression of the terminal linear portion of the log concentration versus time curve
- $t_{1/2}$  Apparent terminal half-life calculated as  $\ln(2)/K_{el}$

PK parameters and the plasma level-versus-time curves will be determined for each evaluable patient. Descriptive statistics including mean, standard deviation, coefficient of variation, median, minimum, maximum, mean and median plasma level graphs will be provided as appropriate.

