Physical examination	X				X				
Vital signs	X				X				
Performance status	X				X				
Height, weight, growth curve	X				X				
Pregnancy test									
Serum chemistry	X				X				
Hematology	X				X				
Urinalysis	X								
Total trough erythrocyte dAXP	X		X		X		X	X	
Trough ADA activity	X ^d		X		X		X	X	
Full PK profile ^e									
B-/T-/NK-lymphocyte subset	X								
Quantitative immunoglobulins	X								
Antibody titers (binding, neutralizing), anti-PEG antibodies	X		X						
Clinical status									
Infectious complications	X	X	X	X	X	X	X	X	
Hospitalizations									
Adverse Events									
Concomitant medications/procedures	X	X	X	X	X	X	X	X	
Adagen [®] administration (± 1 day)									
EZN-2279 administration (± 1 day)	X	X	X	X	X	X	X	X	X

d – trough sample for ADA activity is also the 168 hour full PK sample

e – prior to week T-9 if necessary based upon dAXP and ADA results from weeks T-7 and T-8; if adjustment made, patients return to week T-5

Procedure	EZN-2279 Treatment Period (Weeks 9 through 13)										
	Week T-9							Week T-10	Week T-11	Week T-12	Week T-13
	Day 57	Day 58	Day 59	Day 60	Day 61	Day 62	Day 63	Day 64	Day 71	Day 78	Day 85
Informed assent/consent											
Demographics											
Disease background/history											
Prior Treatments											
Adagen® Dose											
Adagen® AEs											
Infectious complications											
Hospitalizations											
Medical history											
Medication history											
Physical examination	X										X
Vital signs	X										X
Performance status	X										X
Height, weight, growth curve	X										X
Pregnancy test											
Serum chemistry	X										X
Hematology	X										X
Urinalysis											
Total trough erythrocyte dAXP	X							X	X		X
Trough ADA activity	X							X ^f	X		X
Full PK profile ^j	X	X	X	X	X	X	X				
B-/T-/NK-lymphocyte subset	X										
Quantitative immunoglobulins	X										
Antibody titers (binding, neutralizing), anti-PEG antibodies								X			
Clinical status											
Infectious complications	X							X	X		X
Hospitalizations											
Adverse Events											
Concomitant medications/procedures	X							X	X		X
Adagen® administration (± 1 day)											
EZN-2279 administration (± 1 day)	X							X	X	X	X

f – trough sample for ADA activity is also the 168 hour full PK sample

j – Full PK profile conducted only on patients ≥ 10 years of age. Patients < 10 years of age will have limited PK sampling of trough and 48 hour post dosing only.

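### AUC(0-t) has no fixed end point: profiles stopping at 120 h may be combined with 168 h profiles, and SAP 4.2 does not settle which PK summaries under-10s enter

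*SAP*

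**What the plan says.** **AUC definition.** Protocol 13.2.3.6 defines AUC(0-t) as "AUC calculated using linear trapezoidal summation from time zero to time t, where t is the time of the last measurable concentration". Parameters are derived for each evaluable patient and then summarised by mean, standard deviation, coefficient of variation, median and range. Neither document defines an AUC over a common interval.

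**Sufficiency rule.** SAP 4.2 states: "Patient datasets with samples collected until at least 120hr following dosing of EZN-2279 in Week T-9 will be considered sufficient for PK analysis". It names EZN-2279 at Week T-9 only. Protocol 13.2.2 asks for sufficient PK data on two occasions (there labelled Weeks 5 and 13), but the SAP has no equivalent criterion for the Adagen profile.

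**Sampling.** Patients aged 10 or over are sampled before the dose and every 24 h to 168 h, for both products (Protocol 11.2.3.2, 11.3.9 and 11.3.10). The last point needs no extra draw. The SAP's schedule notes for Weeks T-1 and T-10 say that the "trough sample for ADA activity is also the 168 hour full PK sample".

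**Under-10s.** Protocol 10.6.1 says "Only trough samples along with 48 hours post dose during Adagen Lead In Week T-5 and EZN-2279 Week T-9 will be collected". Protocol 6.3.3 computes all PK parameters from full PK sampling and adds that under-10s will not have it. SAP 4.2 builds the set from patients with at least 9 weeks of EZN-2279 "and who have PK data at study week T-9 to indicate exposure, will be the analysis set for evaluating PK parameters". It notes that under-10s "will only have limited sampling done", but it neither excludes them nor says which parameters they contribute to.

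**The concern.** At steady state on a weekly schedule, the AUC that compares patients or products is the one over the 168 h dosing interval. AUC(0-t) equals it only when the last sample is the 168 h one. SAP 4.2 accepts a profile that covers 120 of those 168 hours and does not say how its AUC is to be combined with a complete one.

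The PK profile is a secondary objective, and each patient is his or her own control. Suppose the EZN-2279 profile stops at 120 h and the same patient's Adagen profile reaches 168 h. The two AUCs would then differ through sampling alone. In a set of about six, one such profile also moves the mean.

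The second issue is one of alignment. Read alone, SAP 4.2 admits a three-sample under-10 profile to the set used for PK parameters. Read with Protocol 6.3.3, it should not supply them. The programmer needs to know which reading applies.

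**Working it through.** The plan gives no figure to reproduce here, so the check has two parts: reading the rules together, and an illustrative calculation.

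**1. What the rules allow**

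| Profile | Samples (h) | Meets the 120 h rule? | Interval of AUC(0-t) |
|---|---|---|---|
| Age 10 or over, complete | 0, 24, 48, 72, 96, 120, 144, 168 | Yes | 0-168 |
| Age 10 or over, 168 h missing | 0 to 144 | Yes | 0-144 |
| Age 10 or over, 144 and 168 h missing | 0 to 120 | Yes | 0-120 |
| Under 10 | 0, 48, 168 | Yes, through the 168 h trough | 0-168, from three points |

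An under-10 profile peaking at 48 h has one later sample. SAP 4.2 treats fewer than three points after the peak as insufficient for the terminal phase, so Kel and half-life drop out. No criterion removes Cmax, tmax or AUC(0-t).

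**2. Size of truncation**

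Inputs:
- dosing interval τ = 168 h (Protocol 10.7.3, weekly);
- linear trapezoid (Protocol 13.2.3.6);
- elimination half-lives of 68-79 h (Adagen) and 128-154 h (EZN-2279), which are the dog values in Protocol 5.3.1.2, used because no human value is given;
- absorption half-lives of 6 to 36 h, an assumption.

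Steady-state one-compartment profile, up to a constant:

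C(t) = ka/(ka − k) × [e^(−kt)/(1 − e^(−kτ)) − e^(−ka·t)/(1 − e^(−ka·τ))], with k and ka equal to ln 2 divided by the respective half-life.

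*Worked case: elimination 128 h, absorption 12 h.* The values at 0, 24, …, 168 h are 0.7436, 1.3462, 1.3554, 1.2335, 1.0940, 0.9634, 0.8467 and 0.7436.
- AUC(0-168) = 24 × (0.3718 + 1.3462 + 1.3554 + 1.2335 + 1.0940 + 0.9634 + 0.8467 + 0.3718) = 182.0
- AUC(0-120) = 24 × (0.3718 + 1.3462 + 1.3554 + 1.2335 + 1.0940 + 0.4817) = 141.2
- Ratio = 141.2/182.0 = 0.776, a deficit of 22%

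*Range over the assumed absorption half-lives:*

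| Elimination half-life (h) | AUC(0-120)/AUC(0-168) | AUC(0-144)/AUC(0-168) |
|---|---|---|
| 68 | 0.772-0.839 | 0.896-0.929 |
| 79 | 0.764-0.823 | 0.891-0.921 |
| 128 | 0.745-0.784 | 0.879-0.899 |
| 154 | 0.739-0.773 | 0.875-0.892 |

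The deficit at 120 h is therefore 16 to 26%. It reaches 28% (ratio 0.72) if the peak is as late as 72 h at a 154 h half-life. A flat profile would give 120/168 = 0.71. All peaks fell well before 120 h, so stopping there changes neither Cmax nor tmax.

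*Effect on a mean of six, with equal true AUCs:* shift = (1 − ratio)/6 per truncated profile.
- Ratios 0.82 and 0.75 give 0.18/6 = 3.0% and 0.25/6 = 4.2%.
- The ends of the range give 0.16/6 = 2.7% and 0.28/6 = 4.7%.
- Two truncated profiles double these, to about 6 to 8% in the central range.

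**3. Three-sample profile, if it were summarised**

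Over the absorption half-lives of 6 to 36 h, its AUC is 0.94 to 0.97 of the eight-point AUC, and its Cmax is 0.83 to 1.00 of the eight-point Cmax. The Cmax loss in that grid arises only when the sampled peak is at 24 h. Its tmax is 48 h in every scenario, whatever the true peak time.

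**The case against.** The case for leaving this alone is substantial.

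- **Truncation is a contingency.** By schedule every profile ends at 168 h, and that sample is the pre-dose trough at Week T-1 or T-10. Trough activity is checked against 15 µmol/h/mL at Weeks T-7 and T-8, so an unmeasurable 168 h value is unlikely. This stands: the problem arises only if late samples are missing. But SAP 4.2 provides for that case and leaves its handling open.
- **The effect on the mean is modest.** The 16 to 28% is one patient's deficit. A reader might take it as the error in the summary, but the mean moves by about 3 to 4% per truncated profile in six.
- **Cmax and tmax.** A reader might infer that the 120 h rule distorts these too. It does not; any problem with them could come only from sparse sampling.
- **Under-10s.** A reader might infer that their profiles are averaged with full ones. The documents do not establish this. Protocol 6.3.3 points the other way, Protocol 7.6 describes repeated-sampling PK for patients aged 10 or over, and membership of an analysis set does not mean contributing to every parameter. What remains is that SAP 4.2 does not carry the restriction.
- **Dose normalisation.** A reader might also ask for dose-normalised Cmax and AUC. That is a preference, because each EZN-2279 dose is converted from the patient's own Adagen dose.
- **The PK analysis plan.** SAP section 8 refers to Appendix A for the full PK methods. It is a separate document that was not available and may already settle these points.

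**Conclusion.** The point holds in limited form and with moderate confidence. The visible text fixes no common AUC interval, accepts EZN-2279 profiles ending at 120 h, and has no matching SAP rule for Adagen. AUCs over 120, 144 and 168 h may therefore be averaged or compared if late samples are missing.

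On the stated assumptions, this understates the affected patient's AUC by about 16 to 28% at 120 h and 7 to 13% at 144 h (ratios 0.929 to 0.875). These sizes rest on dog half-lives, an assumed absorption model and a set of six; more than six patients may be enrolled. They are illustrative.

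For under-10s the finding is an inconsistency between SAP 4.2 and Protocol 6.3.3, with no shown error in any summary. If they were included, their tmax would be 48 h by design.

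PK is descriptive here and does not bear on the primary endpoint. This is an inexpensive improvement to make before analysis.

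**What to change.** 1. In Protocol 13.2.3.6 and SAP 4.2, make AUC(0-168 h) the summary exposure measure for both products. State how it is computed when the last sample is not at exactly 168 h, since PK samples have a ±4 h window and the Week T-10 visit has ±1 day.
2. Where the 168 h sample is missing, either extend to 168 h with the patient's own Kel and flag the value, or exclude that AUC. Both options are needed. A 120 h profile peaking at 48 h leaves three later samples (72, 96, 120 h) and meets the SAP's minimum for the terminal phase; one peaking at 72 h leaves two and does not.
3. Apply the same sufficiency rule to the Adagen profile.
4. Align SAP 4.2 with Protocol 6.3.3: limit Cmax, tmax and AUC summaries to full profiles, and report 48 h and trough activity separately for under-10s.
5. Check Appendix A against the revised wording.

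The cost is text changes in the protocol, the SAP and, if needed, the PK plan, with no new blood samples. The downside is fewer patients in some parameter summaries.

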4.3 Completer Population

The completer population, defined as all patients who have received EZN-2279 through the primary endpoint visit (i.e., through Week T-21) will be the analysis set for evaluating efficacy endpoints because the complete EZN-2279 treatment period is required to establish maintenance of the target trough levels, immune function status and other efficacy endpoints.

5. STUDY POPULATION SUMMARY AT SCREENING

The study population will be summarized based on the as-treated population. All summaries in this section describe the patients at the end of the screening period. All study population data will be listed.

5.1 Changes to the Planned Population Summarization Proposed in Protocol

None.

5.2 Patient Disposition

Patients screened, patients enrolled, patients in the as-treated, PK, and completer populations, patients who completed the study, and patients who withdrew from the study will be summarized using descriptive statistics. Patients who withdrew from the study will also be summarized using descriptive statistics by reason for withdrawal.

5.3 Demographics

Demographics will be examined at the end of the screening period. The continuous variables of patient's age, weight, height, and body mass index (BMI) will be summarized using descriptive statistics. The categorical variables of patient's gender, race, and ethnicity will be summarized using descriptive statistics for each category. Growth curve percentiles for height, weight and BMI will also be calculated and summarized while patients are 18 years of age and younger. Missing categories will be presented if applicable.

5.4 Disease Background and History

Disease background will also be summarized at screening. Missing categories will be presented if applicable. Disease background includes ADA-SCID diagnosis and current dose of Adagen[®], prior treatments for SCID including Adagen[®], prior Adagen[®] toxicities in the past year, infectious complications, and hospitalizations.

5.5 Medical History

Medical history at screening will be listed, but not summarized.

5.6 Prior Medications

All prior medications will be coded using the World Health Organization dictionary of medical codes (WHO Drug), Version 2013 Q1, or most recent version prior to database lock. The frequency of prior medications will be summarized using descriptive statistics by therapeutic class and preferred term. Patients are counted only once in each

therapeutic class category, and only once in each preferred term category. Prior medications will include all medications taken prior to the first day of Adagen[®] study drug, in addition to prior to lead in Adagen[®] drug.

5.7 Physical Examination

Physical examination data, including that collected at screening will be listed, but not summarized, as described in Section 7.6.

5.8 Protocol Deviations

A full list of protocol deviations will be compiled and reviewed by the clinical team to identify major versus minor violations/deviations. For violations at study entry, patients will be assessed against the inclusion and exclusion criteria of the protocol. For on-study deviations, compliance with the protocol will be examined using review of the database with regard to prohibited therapies, and timing and availability of planned assessments. Protocol deviations will be listed but not summarized.

6. EFFICACY ANALYSIS

The completer population will be used for the primary efficacy analysis, because the endpoint cannot be evaluated until T-21, and the as-treated population will be used for a sensitivity analysis of the primary efficacy endpoint. The as-treated population will be used for all other efficacy analyses, unless otherwise noted. Summaries will only be presented for the EZN-2279 group. Efficacy is evaluated in comparison to the Adagen® Lead in period ('baseline'). All efficacy data will be listed.

Given the sample size, all efficacy analyses will be descriptive (i.e., no statistical testing and no reported p-values), although 95% confidence intervals (CI) may be presented to show the variability of estimates.

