### 9.5.1. Withdrawal Criteria

Reasons for patient withdrawal or completion of the maintenance period may include the following:

- Adverse event requiring the discontinuation of EZN-2279 treatment
- Death
- Protocol violation requiring the discontinuation of EZN-2279 treatment
- Loss to follow-up
- Withdrawal of consent
- Investigator’s decision, e.g., PI believes it is no longer in the patient’s best interest to remain in the study
- Sponsor’s decision to discontinue the study
- Lack of efficacy
- Study completion (only applies to patients in the maintenance period)
- Other reason - causes of premature termination from the study other than the above (e.g., subject relocated)

The reason for study discontinuation must be documented in the patient’s source documents and in the CRF.

The study will end upon full regulatory approval of EZN-2279 or early study termination of the study by Leadiant Biosciences.

As required, a patient will be followed up after the day of withdrawal, as described below in this section, in Section 11.5, Section 11.5.1 and Section 10.4.4.

Patients are free to withdraw from the study at any time for any reason. Leadiant Biosciences reserves the right to discontinue this study at any time.

The reasons for patient withdrawal or study completion, as well as details relevant to the patient withdrawal or study completion, shall be recorded in the CRF. Patients withdrawn before their completion of the study will undergo all procedures scheduled for study completion as outlined in Section 11.5.

Any patient withdrawn due to any AE (whether serious or non-serious) or clinically significant abnormal laboratory test values will be evaluated by the PI or his/her designee, or a monitoring physician, and will be treated and/or followed up until the symptoms or values return to normal or acceptable levels, as judged by the Investigator (see Section 10.4.4).

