### 9.5.3. Replacement of Discontinued Patients

Patients who do not complete through EZN-2279 Week T-9 will be replaced. Additionally, any patient not completing the EZN-2279 treatment phase of the protocol (i.e. completion of Week T-21) will be considered unevaluable and will need to be replaced to achieve 6 evaluable patients.

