6.2 Primary Endpoint and Analysis

The primary endpoint is the proportion of patients achieving metabolic detoxification, assessed from trough dAXP samples obtained at Weeks T-15, T-17, T-19, and T-21. Metabolic detoxification is defined as a trough dAXP concentration equal to or below 0.02 µmol/mL.

Trough dAXP level will be summarized at each above time point. Maintenance of detoxification is defined as meeting the target trough levels for each of the 4 weeks listed above in the EZN-2279 treatment period. The proportion of patients meeting this definition of maintenance will be summarized.

Trough dAXP level will be summarized at last observed value as a sensitivity analysis using the as-treated population.

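### The primary responder proportion counts only patients dosed through Week T-21, so a failure that ends in discontinuation leaves it, and the visible SAP text specifies no proportion over all EZN-2279-treated patients

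*SAP*

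**What the plan says.** The primary endpoint is the proportion of patients with trough dAXP at or below 0.02 µmol/mL, assessed at T-15, T-17, T-19 and T-21. SAP 6.2 adds: "Maintenance of detoxification is defined as meeting the target trough levels for each of the 4 weeks listed above".

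The analysis set is restricted. SAP 6: "The completer population will be used for the primary efficacy analysis, because the endpoint cannot be evaluated until T-21". SAP 4.3 defines that set: "all patients who have received EZN-2279 through the primary endpoint visit (i.e., through Week T-21) will be the analysis set for evaluating efficacy endpoints".

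Protocol 9.5.3 takes the same line on evaluability: "any patient not completing the EZN-2279 treatment phase of the protocol (i.e. completion of Week T-21) will be considered unevaluable". Such patients are replaced until six are evaluable, with no distinction by reason. The withdrawal reasons in Protocol 9.5.1 include adverse event, death and "Lack of efficacy". The one entry tied to a later period is "Study completion (only applies to patients in the maintenance period"), so the others can apply before T-21.

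On sensitivity, SAP 6 says that "the as-treated population will be used for a sensitivity analysis of the primary efficacy endpoint". SAP 6.2, where the analysis is specified, says: "Trough dAXP level will be summarized at last observed value as a sensitivity analysis using the as-treated population".

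Three other provisions bear on the point:
- Protocol 11.5 asks for a dAXP sample at discontinuation whenever possible.
- SAP 10.4 puts early-termination data into endpoint summaries but not by-visit summaries, and does not impute missing data.
- SAP 5.2 summarizes withdrawals by reason.

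**The concern.** The study asks whether patients already detoxified on Adagen stay so after the switch. Restricting the proportion to patients who reach T-21 conditions the result on something the outcome can influence. A patient withdrawn for lack of efficacy, or withdrawn after a high trough at T-15, is removed and replaced by someone else.

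The SAP's stated reason supports only half of the restriction. Success cannot be confirmed before T-21, because all four visits are needed. Failure can be established earlier: under the four-visit rule, one value above 0.02 µmol/mL at T-15 already settles it.

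Protocol 13.1 plans for a 100% success rate. With about six patients, one failure lost in this way is the difference between reporting 100% and reporting less.

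**Working it through.** **The plan's own figure.** Six patients has no power or precision calculation behind it. The checkable part is the share of the worldwide population: 6/98 = 6.1%, using the roughly 98 patients on Adagen in Protocol 5.1.1.3, which agrees with the stated figure of more than 5%. The 100% success rate in Protocol 13.1 is an expectation and cannot be re-derived.

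**Step 1: who is counted.** Four EZN-2279-treated patients under the current text:
- Above 0.02 µmol/mL at T-17, dosed through T-21: in the denominator, counted as a failure.
- Off target at T-7 and T-8 and not considered fully detoxified: dose adjusted and returned to T-5 (Protocol 11.3.8.1), not removed.
- Above 0.02 µmol/mL at T-15, then withdrawn: in neither numerator nor denominator, and replaced.
- Withdrawn before T-21 for lack of efficacy, an adverse event or death: the same.

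The gap is confined to the last two.

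**Step 2: whether the sensitivity analysis covers them.** The endpoint is a proportion and the specified summary is a concentration. No responder rule is given for a patient without all four visits. A patient above target at T-15 whose last sample before withdrawal was on target would even look favourable in it. The as-treated set (SAP 4.1) also includes patients given only lead-in Adagen, so the matching denominator is patients with at least one EZN-2279 dose.

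**Step 3: size.** The documents give no discontinuation rate, so k, the number of treated failures who stop before T-21, is an assumption. Suppose all six completers succeed.
- Completer proportion: 6/6 for every k.
- All EZN-2279-treated proportion: 6/(6 + k).
- Exact (Clopper-Pearson) 95% limits for x of n: lower = Beta quantile at 0.025 with parameters x and n − x + 1; upper = Beta quantile at 0.975 with parameters x + 1 and n − x. When x = n, the lower limit is 0.025^(1/n) and the upper is 100%.

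| k (assumed) | Completers | All EZN-2279-treated |
|---|---|---|
| 0 | 6/6 = 100% (54.1–100) | 6/6 = 100% (54.1–100) |
| 1 | 6/6 = 100% (54.1–100) | 6/7 = 85.7% (42.1–99.6) |
| 2 | 6/6 = 100% (54.1–100) | 6/8 = 75.0% (34.9–96.8) |

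**Step 4: the bias in expectation.** Let p be the true responder rate and f the share of failures who stop before T-21, and assume every responder completes. The expected completer proportion is p / [p + (1 − p)(1 − f)]. With p = 0.80 as an assumption:
- f = 0: 0.80/1.00 = 80%
- f = 0.5: 0.80/(0.80 + 0.20 × 0.5) = 88.9%
- f = 1: 0.80/0.80 = 100%

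**Step 5: discontinuers for other reasons.** If they have no observed T-15 to T-21 value above 0.02 µmol/mL, counting them as achieving gives 7/7 = 100% (59.0–100) for one and 8/8 = 100% (63.1–100) for two. Counting them as not achieving gives 6/7 and 6/8 as in the table. The distance between the two shows how much rests on the convention.

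**The case against.** The strongest reply is that little is hidden and nothing formal depends on this. Efficacy is descriptive, with no testing. A discontinuer's final dAXP is to be sampled where possible and enters the endpoint summaries, withdrawals are tabulated by reason, and all efficacy data are listed. With seven or eight patients, an attentive reader would see the failure. That is correct, and it limits the point to what the headline proportion counts.

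Protocol 10.7.2 also allows dose or schedule adjustment after consecutive off-target values, so withdrawal is not the only route for a patient with high dAXP. This makes the problem less likely but does not remove it, since lack of efficacy is a listed withdrawal reason.

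Counting an adverse event or a death with on-target dAXP as failure of a biochemical endpoint is a choice of estimand, not a correction of fact. That stands, and is why two versions of the proportion should be shown.

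Three stronger readings are tempting, and the documents do not support them:
- A reader might infer that no all-treated proportion will be produced anywhere. The table shells are in a companion document (SAP Appendix B) that is not part of the material. What can be said is that the visible text specifies none and that SAP 6 and 6.2 do not agree.
- A reader might infer that any patient above target is dropped. A patient who stays through T-21 is counted as a failure.
- A reader might extend the point to completers missing one sample, or to patients still short of T-21 at the three-patient look. Those are separate questions. Neither is a measure of this bias, and SAP 6.4 defers the interim analysis to a BLA SAP.

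**Conclusion.** The point holds and should be fixed. The completer restriction and the replacement rule together remove treated patients whose failure ends in discontinuation, which biases the headline rate upward. The sensitivity analysis as specified does not restore them to a proportion.

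The size depends on how many such patients there are, which the documents do not say: none if nobody discontinues, 14.3 percentage points for one (100 − 85.7) and 25.0 for two (100 − 75.0), given six successful completers. The intervals overlap widely, and 100% is a planning expectation, not a success criterion. A reader might infer that the trial's conclusion would be overturned; with no test and no threshold in the plan, that does not follow. What changes is whether the report says that every patient kept detoxification.

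Treating a single high value as failure assumes that the four-visit proportion is the primary one. Protocol 13.2.2 supports this by requiring the target to be both reached and held, but SAP 6.2 does not say so outright.

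**What to change.** Amend SAP 6 and 6.2 so that they agree:
1. Make the sensitivity analysis of the primary endpoint the four-visit responder proportion, with exact 95% CI, among all patients who received at least one EZN-2279 dose, including those later replaced. Count discontinuation before T-21 as not achieving.
2. Print it directly beside the completer proportion. The completer result may stay the labelled primary analysis, so Protocol 9.5.3 and 13.1 need no amendment.
3. Because item 1 is conservative, add a second version. In it, a discontinuer counts as a failure only with an observed T-15 to T-21 trough dAXP above 0.02 µmol/mL, or a recorded withdrawal reason of lack of efficacy, adverse event or death. Other discontinuers count as achieving.
4. At any look before all patients reach T-21, list patients still on treatment as not yet evaluable, so that the rule in item 1 does not score them as failures.
5. Keep the last-observed dAXP level summary as supportive.

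The cost is SAP wording and one extra set of table rows, using data already collected. The drawback is a possibly less favourable rate. Showing the versions side by side lets the reader judge how much of any drop comes from the convention.
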